#### 10.4.2 General guidelines for reporting adverse events

- All AEs, regardless of seriousness or relationship to IMP/NIMP, spanning from the signature of the informed consent form until the end of the study as defined by the protocol for that patient, are to be recorded on the corresponding page(s) or screen(s) of the e-CRF.
- Whenever possible, diagnosis or single syndrome should be reported instead of symptoms. The Investigator should specify the date of onset, intensity, action taken with respect to

IMP, corrective treatment/therapy given, additional investigations performed, outcome, and his/her opinion as to whether there is a reasonable possibility that the AE was caused by the IMP or by the study procedure(s).

- The Investigator should take appropriate measures to follow all AEs until clinical recovery is complete and laboratory results have returned to normal, or until progression has been stabilized, or until death, in order to ensure the safety of the patients. This may imply that observations will continue beyond the last planned visit per protocol, and that additional investigations may be requested by the monitoring team up to as noticed by the Sponsor.
- When treatment is prematurely discontinued, the patient's observations will continue until the end of the study as defined by the protocol for that patient.
- Laboratory, vital signs or ECG abnormalities are to be recorded as AEs only if:
  - Symptomatic and/or
  - Requiring either corrective treatment or consultation, and/or
  - Leading to IMP discontinuation or modification of dosing, and/or
  - Fulfilling a seriousness criterion, and/or
  - Defined as an AESI

Instructions for AE reporting are summarized in Table 3

# 10.4.3 Instructions for reporting serious adverse events

In the case of occurrence of an SAE, the Investigator or any designees must immediately:

- ENTER (within 24 hours) the information related to the SAE in the appropriate screens of the e-CRF; the system will automatically send a notification to the monitoring team after approval of the Investigator within the e-CRF or after a standard delay.
- SEND (preferably by fax or e-mail) a photocopy of all examinations carried out and the dates on which these examinations were performed, to the representative of the monitoring team whose name, fax number, and email address appear on the clinical trial protocol. Care should be taken to ensure that the patient's identity is protected and the patient's identifiers in the clinical trial are properly mentioned on any copy of a source document provided to the Sponsor. For laboratory results, include the laboratory normal ranges.
- All further data updates should be recorded in the e-CRF as appropriate, and further documentation as well as additional information (for laboratory data, concomitant medications, patient status, etc) should be sent (by fax or e-mail) to the monitoring team within 24 hours of knowledge of the SAE. In addition, every effort should be made to further document any SAE that is fatal or life threatening within a week (7 days) of the initial notification.
- A back-up plan (using a paper CRF process) is available and should be used when the e-CRF system does not work.

Any SAE brought to the attention of the Investigator at any time after the end of the study for the patient and considered by him/her to be caused by the IMP with a reasonable possibility, should be reported to the monitoring team.

## 10.4.4 Guidelines for reporting adverse events of special interest

For AESIs, the Sponsor must be informed immediately (ie, within 24 hours), as per SAE notification guidelines described in Section 10.4.3, even if not fulfilling a seriousness criterion, using the corresponding pages of the CRF (to be sent) or screens in the e-CRF.

Instructions for AE reporting are summarized in Table 3.

Event category	Reporting timeframe	Specific events in this category	Case Report Form completion		
			AE form	Safety Comple- mentary Form	Other specific forms
Adverse Event (non- SAE, non-AESI)	Routine	Any AE that is not SAE or AESI	Yes	No	No
Serious Adverse Event (non-AESI or AESI)	Expedited (within 24 hours)	Any AE meeting seriousness criterion per Section 10.4.1.2	Yes	Yes	No
Adverse Event of Special Interest with immediate notification	Expedited (within 24 hours)	ALT $\geq$ 3 ULN (if baseline ALT <uln) alt<math="" and="">\geq2 x baseline (if baseline ALT<math>\geq</math>ULN)</uln)>	Yes	No	Yes
		Pregnancy	Yes	Yes	Yes
		Symptomatic overdose	Yes	Yes	No

#### Table 3 - Summary of adverse event reporting instructions

Note: Hypoglycemia will be reported on the dedicated hypoglycemia event page. AESI: Adverse Event of Special Interest

# 10.5 OBLIGATIONS OF THE SPONSOR

During the course of the study, the Sponsor will report in an expedited manner:

- All SAEs those are both unexpected and at least reasonably related to the IMP (SUSAR), to the regulatory authorities, IECs/IRBs as appropriate and to the Investigators.
- All SAEs those are expected and at least reasonably related to the IMPs to the regulatory authorities, according to local regulations.

In this study, some AEs are considered related to the underlying condition (eg, blood glucose increased) and thus will not be considered unexpected as given in the Investigator's Brochure for Toujeo (3) and Product information for Tresiba (5).

Any other AE not listed as an expected event in the Investigator's Brochure or in this protocol will be considered unexpected.

The Sponsor will report all safety observations made during the conduct of the trial in the clinical study report.

# **10.6 SAFETY INSTRUCTIONS**

## 10.6.1 Hypoglycemia

Hypoglycemia events will be categorized as follows according to ADA category (17):

#### Severe hypoglycemia

Severe hypoglycemia is an event requiring assistance of another person to actively administer carbohydrate, glucagon, or other resuscitative actions. These episodes may be associated with sufficient neuroglycopenia to induce seizure, unconsciousness or coma. Plasma glucose measurements may not be available during such an event, but neurological recovery attributable to the restoration of plasma glucose to normal is considered sufficient evidence that the event was induced by a low plasma glucose concentration.

The definition of severe hypoglycemia includes all episodes in which neurological impairment was severe enough to prevent self-treatment and which were thus thought to place patients at risk for injury to themselves or others.

**Note** that "requires assistance" means that the patient could not help himself or herself. Assisting a patient out of kindness, when assistance is not required, should not be considered a "requires assistance" incident.

Severe hypoglycemia will be qualified as an SAE only if it fulfills SAE criteria. All events of seizure, unconsciousness or coma must be reported as SAEs.

# Documented symptomatic hypoglycemia

Documented symptomatic hypoglycemia is an event during which typical symptoms of hypoglycemia are accompanied by a measured plasma glucose concentration of  $\leq$ 70 mg/dL (3.9 mmol/L).

Clinical symptoms that are considered to result from a hypoglycemic episode can include (but not necessarily limited to): increased sweating, nervousness, asthenia, tremor, dizziness, increased appetite, palpitations, headache, sleep disorder, confusion, seizures, unconsciousness, and coma. Patients will be instructed to measure finger stick plasma glucose levels prior to the administration of carbohydrates whenever symptomatic hypoglycemia is suspected, unless safety considerations necessitate immediate glucose rescue prior to confirmation, and then a glucose measurement should be performed as soon as safe, with appropriate diary documentation. Details on hypoglycemia episodes will be captured in the patient diaries, and patients will contact the sites as soon as possible following severe events to review the details and decide on any necessary measures to be taken.

# Asymptomatic hypoglycemia

Asymptomatic hypoglycemia is an event not accompanied by typical symptoms of hypoglycemia but with a measured plasma glucose concentration less than or equal to 70 mg/dL (3.9 mmol/L).

#### Probable symptomatic hypoglycemia

Probable symptomatic hypoglycemia is an event during which symptoms typical of hypoglycemia are not accompanied by a plasma glucose determination, but was presumably caused by a plasma glucose concentration less than or equal to 70 mg/dL (3.9 mmol/L); symptoms treated with oral carbohydrate without a test of plasma glucose.

#### Pseudo hypoglycemia

Pseudo-hypoglycemia is an event during which the person with diabetes reports any of the typical symptoms of hypoglycemia with a measured plasma glucose concentration >70 mg/dL (>3.9 mmol/L) but approaching that level.

#### Nocturnal hypoglycemia

Nocturnal hypoglycemia is any hypoglycemia of the above categories that occurs:

- Between 00:00 AM and 05:59 AM or 00:00 AM and 7:59 AM, regardless whether patient was awake or work up because of the event.
- Sleep status: patient was asleep between bedtime and before getting up in the morning, ie, before the morning determination of fasting pre-breakfast SMPG and patient woke-up due to the hypoglycemia

Note: **Confirmed hypoglycemia:** Any hypoglycemia confirmed by plasma glucose value below the cut off value (1) of 70 mg/dL (3.9 mmol/L) or (2) 54 mg/dL (3 mmol/L).

All hypoglycemia episodes will be documented on the dedicated hypoglycemia event page in the e-CRF. Symptomatic hypoglycemia events fulfilling the criteria of a SAE will also be documented on AE and SAE complementary forms in the e-CRF.

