Kaplan-Meier (KM) plots/estimates of the cumulative incidence of IMP discontinuation due to any reason will be provided. Time to treatment discontinuation is defined as the number of days from the first dose of IMP until the day of treatment discontinuation. All completers are considered as censored observations. The censoring time is the number of days from the first dose of IMP until the last dosing date.

Kaplan-Meier (KM) plots/estimates of the cumulative incidence of IMP discontinuation due to adverse event will be provided. Time to treatment discontinuation is defined as the number of days from the first dose of IMP until the day of treatment discontinuation. All completers are considered as censored observations. The censoring time is the number of days from the first dose of IMP until the last dosing date.Kaplan-Meier (KM) plots/estimates of the cumulative incidence of study discontinuation due to any reason will be provided. Time to study discontinuation is defined as the number of days from the randomization date until the day of study discontinuation. All completers are considered as censored observations. The censoring time is the number of days from the randomization date until the day of study discontinuation. All completers are considered as censored observations. The censoring time is the number of days from the randomization date until the last day of study discontinuation.

All critical or major deviations potentially impacting efficacy analyses, randomization, and drug-dispensing irregularities, and other major or critical deviations will be summarized in tables giving numbers and percentages of deviations by treatment group. Patients excluded from the ITT/PP population will be listed as well as patients with major deviation potentially impacting efficacy analyses not resulting in exclusion from ITT or PP populations. These deviations are listed in the data review and surveillance plan.

Additionally, the analysis populations (Section 2.3) for safety and efficacy are summarized in a table by patient counts on the randomized population:

- Efficacy populations: ITT population; Per-Protocol population,
- Safety population.

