• All treatment-emergent adverse events leading to treatment discontinuation, by primary SOC, HLGT, HLT, and PT, showing the number (%) of patients sorted by the internationally agreed SOC order. The other levels (HLGT, HLT, PT) will be presented in alphabetical order.

Analysis of injection site reactions and hypersensitivity reaction TEAE(s)

• All treatment-emergent adverse events related to injection site reactions or hypersensitivity reactions, by PT, showing the number(%) of patients sorted by decreasing incidence of PTs in Toujeo®.

Analysis of adverse events of special interest

• A listing of patients with symptomatic overdose with IMP/NIMP, pregnancy and increase of ALT will be provided separately.

Analysis of pretreatment and post-treatment adverse events

- All pre-treatment adverse events by primary SOC and PT, showing the number (%) of patients with at least 1 pre-treatment adverse event, sorted by the internationally agreed SOC order and decreasing incidence of PTs in Toujeo ® within each SOC,
- All pre-treatment adverse events leading to study discontinuation by primary SOC and PT, showing the number (%) of patients, sorted by the internationally agreed SOC order and decreasing incidence of PTs Toujeo ® within each SOC,
- All post-treatment adverse events by primary SOC and PT, showing the number (%) of patients with at least 1 post-treatment adverse event, sorted by the internationally agreed SOC order and decreasing incidence of PTs Toujeo ® within each SOC,
- All post-treatment serious adverse events by primary SOC and PT, showing the number (%) of patients with at least 1 posttreatment serious adverse event, sorted by the internationally agreed SOC order and decreasing incidence of PTs Toujeo ® within each SOC,
- Listing of SAE,
- Listing of AEs leading to permanent treatment discontinuation.

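### Stops of study insulin caused by non-serious hypoglycemia have no stated route into the tables of TEAEs leading to permanent discontinuation, and no by-arm output of their own

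*Protocol*

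**What the plan says.** **Recording.** Protocol 10.6.1 (closing text under Nocturnal hypoglycemia) states: "All hypoglycemia episodes will be documented on the dedicated hypoglycemia event page in the e-CRF". It continues: "Symptomatic hypoglycemia events fulfilling the criteria of a SAE will also be documented on AE and SAE complementary forms in the e-CRF". The note to Protocol Table 3, which sets out which form each type of event needs, repeats the first rule: "Hypoglycemia will be reported on the dedicated hypoglycemia event page". Severity alone does not change the route, because under Severe hypoglycemia the protocol says "Severe hypoglycemia will be qualified as an SAE only if it fulfills SAE criteria", although seizure, unconsciousness or coma must always be reported as SAEs.

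**Safety outputs.** Protocol 11.4.3.2.2 and SAP 2.4.5.2 plan outputs for adverse events that lead to stopping treatment. The SAP has an overview row, a listing, and a table described as "All treatment-emergent adverse events leading to treatment discontinuation, by primary SOC, HLGT, HLT, and PT". SAP 2.1.4.2 has adverse events coded in MedDRA. Hypoglycemia is analysed separately in SAP 2.4.5.1.

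**Disposition.** SAP 2.2 tabulates permanent discontinuation by main reason and treatment group and lists the patients with a free-text reason. It also plans a Kaplan-Meier output: "cumulative incidence of IMP discontinuation due to adverse event will be provided".

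**The concern.** The tables of adverse events leading to discontinuation are where a reader looks to see which events made patients give up each insulin. A patient who stops because of repeated non-serious hypoglycemia has had an adverse event in the sense of Protocol 10.4.1.1. If the only record of it is the hypoglycemia page, that patient is absent from a table whose title claims to cover all such events.

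The gap falls on the risk that matters most in this comparison. Protocol section 4 singles out the head-to-head hypoglycemia result as being of special interest, and names hypoglycemia among the concerns that hold patients and physicians back from insulin. At stake are the completeness of one family of safety tables and its agreement with the disposition counts.

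**Working it through.** No arithmetic settles this. The question is which record each output draws on, so I followed the recording rules through to the planned tables.

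1. **Which hypoglycemia reaches the AE form?** Protocol 10.6.1 names one group, symptomatic events meeting SAE criteria. Protocol 10.4.1.3 and Table 3 add a second, symptomatic overdose, which is an AESI and goes on the AE form whether serious or not. What is left is hypoglycemia that is neither an SAE nor an AESI.

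2. **Does the general AE rule bring the remainder in?** Protocol 10.4.2 covers all AEs regardless of seriousness, but says that they "are to be recorded on the corresponding page(s) or screen(s) of the e-CRF". For hypoglycemia, Table 3 and 10.6.1 identify that page as the hypoglycemia page. The rule does not lead to the AE form.

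3. **Does stopping treatment trigger an AE record?** Protocol 10.4.2 has such a trigger, but it sits in a list confined to laboratory, vital-sign and ECG abnormalities. Hypoglycemia is not in that list.

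4. **Does the hypoglycemia page supply the link?** Protocol 9.2.1.2.2 says what is recorded for a symptomatic episode: glucose value and time, countermeasures, symptoms and need for assistance. Action taken with the IMP, which 10.4.2 asks for with AEs, is not named.

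5. **Do the hypoglycemia analyses fill the gap?** SAP 2.4.5.1 plans incidence, event rates, results by study period and time of day, subgroups, relative risks and risk differences. None is by discontinuation.

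6. **Where does the stop still appear?** Protocol 10.3, 10.3.3 and 10.3.4 require IMP discontinuation to be recorded in the e-CRF, with every effort to document the reason. SAP 2.2 then tabulates the main reason by arm. Neither document gives the list of reason categories, so a hypoglycemia stop might be coded as an adverse event or otherwise. If it is coded as an adverse event, the disposition table counts a stop for which the SAP 2.4.5.2 table may hold no AE record.

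**Size.** Let *h* be the patients in an arm who stop because of hypoglycemia that is neither an SAE nor an AESI, and *a* those who stop because of other adverse events. The table would show *a* instead of *a + h*, a relative shortfall of *h/(a + h)*. The documents give neither *h* nor *a*, so the shortfall could lie anywhere from nil upward.

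**The case against.** The strongest reply is that these stops are neither uncollected nor unreported. The reason for stopping IMP must be documented, disposition shows reasons by arm, and the free-text listing lets a reader identify hypoglycemia. That stands. A reader might infer that a between-arm difference in hypoglycemia-driven stopping would vanish from the report. The documents do not support that.

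A second reply is that much hypoglycemia does reach the AE form: every seizure, unconsciousness or coma, any event meeting another seriousness criterion, and symptomatic overdose. That also stands. It would be wrong to conclude that the discontinuation tables leave out hypoglycemia as a whole.

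Third, the SAP 2.2 Kaplan-Meier output need not be affected. The SAP does not say whether its reason comes from the disposition page or from AE records. If it comes from disposition, a stop coded as an adverse event is already in the curve.

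Fourth, the restriction is inferred. The protocol says that SAE-level events are documented on the AE form as well; it does not forbid entering others. SAP 2.5.3 treats adverse events and hypoglycemia together when an onset date is missing, and the e-CRF is not shown. This limits certainty about what sites would do. It does not supply the missing instruction, and two sites could follow the text in good faith and record the same stop differently.

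Finally, few patients may be involved, since Protocol 10.3 treats permanent discontinuation as a last resort. That is plausible but cannot be checked.

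**Conclusion.** The point holds as a gap in safety reporting. Followed as written, the outputs for TEAEs leading to permanent discontinuation would omit stops caused by hypoglycemia that is neither an SAE nor an AESI, and no other planned table gives those stops by arm under that name. They remain visible through the main reason and the free-text listing. The residual harm is an incomplete table and a possible disagreement between it and disposition, not a lost signal.

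The conclusion rests on reading Protocol 10.6.1 with the Table 3 note as the full rule for hypoglycemia, and on the AE tables being built from AE records, as the separate treatment in SAP 2.4.5.1 and 2.4.5.2 implies. An e-CRF completion guide that says otherwise would remove the point. The number of patients affected cannot be estimated. The primary non-inferiority analysis does not depend on it. The correction is worth making because it is cheap and concerns the risk on which the protocol lays particular weight.

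**What to change.** **If the e-CRF rules are fixed:** add to SAP 2.4.5.1 or 2.4.5.2 a row by arm for IMP permanently discontinued due to hypoglycemia. Derive it from the end-of-treatment reason, including its free text, together with the hypoglycemia page. The recorded reason should decide, since an episode shortly before the last dose does not by itself show cause. Reconcile the patient counts with the disposition table and the Kaplan-Meier output, and state in SAP 2.2 which record supplies the reason for that output. Compare counts rather than percentages, because disposition uses randomized patients as denominator and the AE tables use the safety population.

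**If the e-CRF rules can still change:** add one sentence to Protocol 10.6.1 and to the Table 3 note requiring the AE form for any hypoglycemia that leads to permanent IMP discontinuation, and include these events in the SAP 2.4.5.2 discontinuation outputs.

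**Cost:** one row or one sentence, some reconciliation work, a few events recorded on two pages, and slightly less favourable AE-discontinuation figures. No hypothesis test or rule of clinical management changes.

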# 10.6.2 Local tolerability at injection site and hypersensitivity reactions

If the investigator or the patient recognizes any signs of local intolerability at the study drug injection site or hypersensitivity reactions, the event should be recorded in the adverse event page in the e-CRF. If a patient reports severe injection site or hypersensitivity reaction between the onsite visits or during a phone call visit, the investigator should ask him/her to come to the study site on the same or the next day, so that the event can be properly assessed, reported and treated.

# 10.7 ADVERSE EVENTS MONITORING

All events will be managed and reported in compliance with all applicable regulations, and included in the final clinical study report.

Property of the Sanofi Group - strictly confidential

# 11 STATISTICAL CONSIDERATIONS

# 11.1 DETERMINATION OF SAMPLE SIZE

The sample size calculation is based on the primary efficacy variable of HbA1c change from baseline to Week 24.

A sample size of 920 randomized patients (460 randomized per treatment group) will ensure that the upper bound of the two-sided 95% confidence interval (CI) for the adjusted mean difference between Toujeo and Tresiba would not exceed a non-inferiority margin of 0.3% with at least 90% power. This calculation assumes a common SD of 1.4% with a 1-sided test at the 2.5% significant level and a true difference between Toujeo and Tresiba is zero in HbA1c between the treatment groups.

Calculations were made using nQuery Advisor® Software Version 7.0.

# 11.2 DISPOSITION OF PATIENTS

The total number of patients for each of the following categories will be presented.

- Screened: all patients who originally met inclusion criteria and signed the informed consent
- Screen failure patients and reason for screen failure
- Randomized: all screened patients with a treatment arm allocated and recorded in the IVRS/IWRS database, regardless of whether the treatment kit was used or not
- Safety population (see Section 11.3.2) presented as treated
- The intent-to-treat (ITT) population (Section 11.3.1.1) analyzed as randomized
- The randomization strata (screening HbA1c categories [<8.0%, ≥8.0%], use of SU or meglitinides at screening [Yes, No]) assigned by IVRS/IWRS will be summarized. The discrepancy between the strata assigned by IVRS/IWRS and the information reported on CRF will be listed for all randomized patients
- The Per-Protocol (PP) population (Section 11.3.1.2 analyzed as subset of ITT population and without major protocol deviations)
- Patients who permanently discontinued the IMP, and the reasons for permanent treatment discontinuation

For all categories of patients except screened and screen failure patients, percentages will be calculated using the number of randomized patients as denominator for different treatment groups.

Patients with the following deviations will be identified and described in separate listings:

- Treated but not randomized
- Randomized but not treated
- Randomized but not treated as randomized

A list of patients prematurely discontinued from the treatment, along with reasons for discontinuation, will be provided.

For any patient randomized more than once, only the data associated with the first randomization will be used in any analysis population. The safety experience associated with any later randomization will be assessed separately.

The safety experience of patients treated and not randomized will be reported separately, and these patients will not be in the safety population.

